10.3 Subgroup Analysis

The primary effectiveness analysis (KM analysis of time to persistent AF/AT) will be performed for the Test Group as randomized and for the Control Group as randomized (excluding cross-over subjects). The cross-over subjects (i.e., continued on their current AAD or taking a newly prescribed AAD and had an RF ablation procedure) will be analyzed separately as a third group.

- Test Group: randomized to RF ablation to achieve PVI using the CARTO[®] 3, CARTO[®] XP or CARTO[®] RMT System, and THERMOCOOL[®] Catheter Family

- Control Group: randomized to AAD therapy in accordance with current AF management guidelines¹⁻³
- Cross-over Group: Control Group subjects who undergo RF ablation to achieve PVI using the CARTO[®] 3, CARTO[®] XP or CARTO[®] RMT System, and THERMOCOOL[®] Catheter Family

If observed, the median time to persistent AF/AT as well as the 95% confidence intervals will be reported for the three groups based on Kaplan-Meier estimates. Kaplan-Meier curves will be plotted. The product limit estimates of the rate of survival without persistent AF/AT and rate of persistent AF/AT at 3 years follow-up as well as the 95% confidence intervals for these three groups will be presented separately.

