#### 13.11.2 Subgroup Analyses

The primary effectiveness analysis (KM analysis of time to persistent AF/AT) will be performed for the Test Group as randomized and for the Control Group as randomized (excluding cross-over subjects). The cross-over subjects (i.e., continued on their current

AAD or taking a newly prescribed AAD and had an RF ablation procedure) will be analyzed separately as a third group.

- Test Group: randomized to RF ablation to achieve PVI using the CARTO® 3, CARTO® XP or CARTO® RMT System, and THERMOCOOL® Catheter Family
- Control Group: randomized to AAD therapy in accordance with current AF management guidelines
- Cross-over Group: Control Group subjects who undergo RF ablation to achieve PVI using the CARTO® 3, CARTO® XP or CARTO® System, and THERMOCOOL® Catheter Family

The median time to persistent AF/AT as well as the 95% confidence intervals will be reported for the three groups. The survival probability and rate of persistent AF/AT at 3 years follow-up as well as the 95% confidence intervals for these three groups will be presented separately.

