6. SAMPLE SIZE DETERMINATION

A total sample size of 322 (161:161) subjects will be required to ensure 85% power to detect the effect size measured by negative log of the hazard ratio equal to 1.1541 (treatment group over control group).

$$-\log_e \left(\frac{\hat{\lambda}_t}{\hat{\lambda}_c} \right) = -\log_e \left(\left(-\frac{\log_e(0.95)}{3} \right) / \left(-\frac{\log_e(0.85)}{3} \right) \right) = 1.1541$$

This calculation assumes a 50% cross-over rate from the AAD group to the ablation group, a 10% drop-out rate in each group over the 3 year follow-up period, and 1.5 years accrual time. This calculation is based upon one-sided superiority testing with alpha equal to 0.025. Using meta-analysis, the rates of disease progression at the end of follow-up are estimated to be 25% and 5% in the AAD and ablation group, respectively (see the point estimate justification document for details, Appendix C of the CTP). The cross-over to ablation is reflected in the use of the proportion 0.85 instead of 0.75 in the formula above. The sample size calculation is based upon the method developed by Rubinstein, Gail and Santner⁴ (RGS, 1981) and also incorporates group sequential design with multiple interim looks.

Adaptive Sample Size Re-estimation

Due to the uncertainties associated with the cross-over rate and the effect size, the sample size will be reestimated at the time of the first interim analysis. Conditional power (CP) will be calculated at that time to determine how promising the interim results are. CP is defined as the conditional probability that the final result will exceed a critical value given the data observed thus far, and the assumption that the trend to be observed in the remainder of the study⁵ will follow the expectation, which was used in the original sample size calculation. If the CP is less than 0.3, then the study is considered not promising, and the sample size will not be increased. If the CP is

greater than 0.9, then the study is deemed fully powered and the sample size will not be increased. If the CP falls in the promising zone (0.3-0.9), the sample size will be re-estimated based upon the observed effect size.

In detail, the following formula will be applied to re-estimate the sample size:

$$M = N \left(\frac{\delta}{\Delta} \right)^2$$

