7. ANALYSIS POPULATIONS

The following analysis populations will be used to complete the analyses of data.

Cross-over subjects will be handled differently for each type of analysis population, as described subsequently. In general, subjects from the control group who have an ablation procedure after the primary endpoint is met will not be analyzed as cross-over.

Intent to treat (ITT) population: The ITT subject population will include all

subjects randomized, where subjects will be classified by the group to which they are randomized, regardless of the treatment received. For the ITT population, cross-over subjects will be included in the Control Group per randomization. Lost-to-follow-up and withdrawn/early termination subjects will also be included in the ITT population.

Per protocol (PP) population: The PP subject population will include randomized subjects who satisfy the following criteria, according to the treatment actually received:

- **Test Group:** subjects who
 - have undergone RF ablation,
 - are treated with the study catheter (THERMOCOOL[®] Catheter Family),
 - are in compliance (no major protocol deviations that has an impact on scientific value of the study) with the study protocol, and
 - have been treated for the study-related arrhythmia.
- **Control Group:** subjects who
 - have started an investigator-prescribed AAD and completed the dose-loading period (2 weeks),
 - have not undergone RF ablation,
 - are in compliance (no major protocol deviations that have an impact on scientific value of the study) with the study protocol, and
 - have been treated for the study-related arrhythmia.

All analyses conducted in the PP population will be as treated analyses. For descriptive tables and simple inferential models with fixed treatment effects subjects who have undergone RF ablation will be included in the Test Group regardless of the original treatment assigned (original randomization). Thus, cross-over subjects will be included in the Test Group for PP analyses. For more complicated inferential analyses, models will be applied where treatment itself is included as time-dependent covariate (see section 10.2 and 10.6.4). The approach described above applies for all tables which do not summarize data by visit (e.g. for time to event endpoints and other endpoints calculated overall per-patient). For summaries by visit and repeated measurement models, cross-over subjects will be completely excluded.

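### SAP 10.3 removes cross-overs from the Control curve as whole subjects, so early progressors stay while event-free drug time leaves, and the three 3-year rates cannot be compared

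*SAP*

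**What the plan says.** SAP 10.3 repeats the primary Kaplan-Meier analysis in three groups. It is "performed for the Test Group as randomized and for the Control Group as randomized (excluding cross-over subjects", with cross-over subjects shown as a third group. Median times, 3-year rates with 95% confidence intervals and curves are reported for each. Protocol 13.11.2 has the same layout; its third group is introduced by the sentence beginning "The cross-over subjects (i.e., continued on their current".

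Three other provisions decide what this grouping does:

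- SAP 7 limits who is a cross-over: "subjects from the control group who have an ablation procedure after the primary endpoint is met will not be analyzed as cross-over". A Control subject who progresses first stays in Control even if ablated later.
- SAP 8.3 starts the clock at the procedure for Test and at randomization for Control. SAP 10.3 gives no separate origin for the cross-over curve, so randomization is inferred from 8.3.
- SAP 10.5 repeats 10.1 to 10.3 with the HRS 2017 definition. The affected outputs are tables 14.2.3.1 and 14.2.3.2 and figures 14.5.2 and 14.5.5.

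SAP 10.3 provides no censoring at cross-over, delayed entry, landmark or caveat. The Cox model in SAP 10.2 treats the same subjects differently: they count as control up to the cross-over and as ablation afterwards.

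**The concern.** Group membership depends on something that happens after time zero and can happen only to subjects who are still event-free. This is guaranteed-time (immortal-time) bias. Taking cross-overs out of Control from randomization removes person-time on drug in which, by definition, no event occurred, and leaves behind every subject who progressed before any ablation. The same event-free time then opens the cross-over curve.

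The SAP expects cross-over to be large and to dilute the effect: "This calculation assumes a 50% cross-over rate from the AAD group to the ablation group", which takes the Control rate used for sizing from 25% to 15%. Test beside Control without cross-overs is therefore an obvious place for a reader to look for an undiluted effect, with 3-year rates and intervals ready to compare.

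**Working it through.** **Inputs (SAP 6).** The 3-year rates are "estimated to be 25% and 5% in the AAD and ablation group, respectively"; cross-over is 50%; there are 161 subjects per arm. Cross-over timing is not specified. Protocol 8.3 cites 42% to 59% within 1 year in earlier studies, so timing is varied below as an assumption.

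**The plan's own figure.** "A total sample size of 322 (161:161) subjects will be required to ensure 85% power to detect the effect size"; "This calculation is based upon one-sided superiority testing with alpha equal to 0.025".

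- Control event-free share: 1 − (0.5 × 0.25 + 0.5 × 0.05) = 0.85, as the SAP uses.
- Effect: −ln[ln(0.95)/ln(0.85)] = 1.1532. The SAP prints "negative log of the hazard ratio equal to 1.1541"; the difference is immaterial.
- With exponential times, follow-up of 3 to 4.5 years and 10% drop-out per 3 years, the event probabilities are 0.0582 (Test) and 0.1723 (Control).
- n per arm = (1.960 + 1.036)² / 1.1532² × (1/0.0582 + 1/0.1723) ≈ 155. The unrounded total is 310.5. Group-sequential inflation of 1.021 to 1.026 gives 317 to 319, against 322.

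The inputs are therefore read as the plan meant them.

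**Independent cross-over.** Let λ = −ln(1 − p)/3 be the progression hazard for a true 3-year drug rate p. Cross-over has constant hazard m on [0, a], unrelated to risk, with m chosen so that 50% actually cross before progressing:

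m/(λ + m) × [1 − exp(−a(λ + m))] = 0.5

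Of the 0.5 who never cross, the event-free share is (1 − p) × exp(−am), and the rest had events. Hence:

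- Control rate shown = [0.5 − (1 − p)exp(−am)] / 0.5
- Cross-over rate shown if ablation does nothing = {p − [0.5 − (1 − p)exp(−am)]} / 0.5

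| True p | Cross-over period | m | exp(−am) | Control shown | Cross-over shown (no ablation effect) |
|---|---|---|---|---|---|
| 25% | 3 years | 0.2769 | 0.4358 | (0.5 − 0.3268)/0.5 = 34.6% | (0.25 − 0.1732)/0.5 = 15.4% |
| 25% | year 1 | 0.7367 | 0.4787 | (0.5 − 0.3590)/0.5 = 28.2% | (0.25 − 0.1410)/0.5 = 21.8% |
| 15% | 3 years | 0.2561 | 0.4638 | (0.5 − 0.3942)/0.5 = 21.2% | (0.15 − 0.1058)/0.5 = 8.8% |
| 15% | year 1 | 0.7175 | 0.4880 | (0.5 − 0.4148)/0.5 = 17.0% | (0.15 − 0.0852)/0.5 = 13.0% |

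The Control column does not depend on whether ablation works, because cross-overs have left that curve. In the first row, about 0.1732 × 161 ≈ 28 events fall among 80.5 subjects. The 15% rows illustrate a null case; in the documents 15% is the diluted Control rate. Leaving Control at cross-over instead gives 1 − exp(−3λ), that is 25.0% or 15.0%.

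**Sensitivity to timing and amount (true rate 25%).** If half of Control is destined to cross at a uniformly distributed time, Control shows 25.0% when cross-over is almost immediate, 26.7% over 6 months and 38.2% when it falls only in year 3. With constant hazard over 3 years, it shows 26.2%, 28.5% and 38.6% at 10%, 25% and 60% cross-over.

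**Risk-related cross-over (simulation, no ablation effect, true rate 25%).** Each subject has a log-normal frailty W. The progression hazard is proportional to W and the cross-over hazard to W^g. About half cross.

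| Timing | SD of log W | g | SAP 10.3 Control | Control censored at cross-over |
|---|---|---|---|---|
| year 1 | 0.5 | 1 | 25.2% | 22.1% |
| year 1 | 1.0 | 1 | 19.0% | 16.2% |
| 3 years | 0.5 | 1 | 31.6% | 23.0% |
| 3 years | 1.0 | 1 | 25.4% | 18.4% |
| 3 years | 1.0 | 2 | 19.2% | 14.8% |

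**The case against.** The strongest objection concerns direction. A reader might infer that the display favours ablation by construction. The documents do not support that. Protocol Appendix B argues that those who seek cross-over may be older and have higher HATCH scores, leaving a younger, healthier and more compliant drug group. Such selection lowers the Control rate. With year-1 timing, moderate selection cancels the inflation and stronger selection reverses it. This stands.

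A reader might also infer that censoring at cross-over recovers the true drug rate. It does so only if cross-over is unrelated to risk. Under risk-related cross-over it is too low, and in four of the five simulated cases it is further from 25% than the planned grouping. This also stands. It is no defence of the grouping, however: where that lands near 25%, two unmeasured errors happen to offset each other.

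The point is also limited in weight. Table 14.2.3.1 lists Kaplan-Meier results without a log-rank test. SAP 10.3 does not claim to show an undiluted effect, so how it will be read is a risk and not a fact. With about 80 subjects left at a rate near 28%, the 95% half-width is about 1.96 × √(0.28 × 0.72/80.5) ≈ 10 points, more than the year-1 bias of about 3. The Cox model in 10.2 already handles the time properly. None of this corrects the curves in 10.3, which carry no warning.

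**Conclusion.** The concern holds in a limited form. SAP 7, 8.3 and 10.3 together create guaranteed-time bias in the three-group display and its HRS 2017 repeat, and this is inconsistent with the SAP's own Cox model in 10.2. If 50% cross independently of risk, the 3-year Control rate shown is about 28% to 35% against a true 25%. With 15% everywhere and no ablation effect it is about 17% to 21%, with the cross-over curve at 9% to 13%.

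These figures assume exponential progression, no drop-out, randomization as the origin of the cross-over curve, and cross-over timing that the documents do not give. The net error could be near zero or reversed. The supported conclusion is that the three rates are not comparable, not that they must flatter ablation. The primary analysis in SAP 10.1 keeps cross-overs in Control and is untouched. The change should be made, but the trial's main conclusion does not depend on it.

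**What to change.** In SAP 10.3 and its HRS 2017 repeat:

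1. Keep Test as randomized. Keep cross-over subjects in Control until their cross-over ablation and let them leave the curve then, as the 10.2 Cox model assigns time.
2. Start the cross-over curve at ablation, or use delayed entry. Drop its 3-year rate counted from randomization.
3. State that leaving Control at cross-over assumes cross-over is unrelated to risk, and that the drug rate may be understated if higher-risk subjects cross.
4. Add a sensitivity version weighted for cross-over on collected covariates such as age and HATCH score.
5. Label the three curves as not a randomized comparison and refer the reader to the time-dependent Cox model in 10.2. Name that model specifically, because the per-protocol Kaplan-Meier analysis moves cross-overs into Test.

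The cost is SAP wording and minor reprogramming of two tables and two figures, plus the weighted version. No new data are needed. The Control curve will rest on a stated assumption, weighting can adjust only for what was collected, and the displayed contrast may become less favourable to ablation.

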10.4 Interim Analysis

To properly account for the repeated interim testing in this study, a group sequential method similar to that proposed by O'Brien and Fleming as a guide in interpreting interim analyses will be used.⁷ This procedure requires large critical values early in the study, but relaxes (i.e., decreases) the critical value as the trial progresses. Because of the conservatism early in the trial, the critical value at the final analysis is near the "nominal" critical value. Hence, the sample size requirements with this group sequential procedure remain essentially the same as the conventional fixed sample size estimate. The actual method for the interim reporting that will be employed in this study is the "alpha-spending function" approach to group sequential testing developed by Lan and DeMets.⁸ The Lan-DeMets approach is flexible to accommodate unequal sized groups with the number of interim looks unspecified in advance. It only requires specification of the rate at which the Type I error (which in this trial will be $\alpha=0.025$ for the primary endpoint) will be "spent". This procedure allows "spending" a portion of α at each interim analysis in such a way that at the end of the study, the total Type I error does not exceed 0.025. This spending function generates boundaries that are nearly identical to the O'Brien-Fleming boundaries.

In survival trials, information time is calculated based upon number of events rather than number of subjects accrued. In practice, interim analyses are often scheduled based upon specified calendar time rather than number of events. To address the logistical inconvenience, Lan and DeMets extended their general group sequential approach for the maximum duration trial.⁹ That is, the conduct of a trial is expected to occur within some period of time $[0, T_c]$, where T_c is the maximum calendar (or duration) time for completion. The stopping boundaries can be adjusted based on the actual number of events observed at the interim look, rather than information fraction. This method allows flexibility in the monitoring process for accommodating any changes in terms of timing and spacing of the looks or additional examination of the data that is not pre-determined in response to the concerns from the GSMC that may arise during the course of the trial.

The analytic approach that will be used for the interim analyses for assessing treatment differences will be the time-to-event analysis method. The standardized log rank score statistic will be compared with the stopping boundaries at each interim look to draw statistical inference. If the stopping boundary is crossed, then the study

will stop for effectiveness.

Judgment concerning the continuation or termination of the study will involve not only the degree of statistical significance observed at the interim analysis, but also the likelihood of achieving significance should enrollment continue to the originally projected sample size. As an aid in this latter assessment, the group sequential analyses outlined above will be supplemented with calculations of conditional power. Conditional power (CP) for the primary treatment comparison will be provided to the GSMC as a regular part of the interim study reports. If the CP is less than 0.3, then the study will be stopped for futility.

The time points of the interim analyses and the number of interim analyses are not fixed in advance. The table below contains an example, based on initially estimated study times. The example assumes a first interim analysis after 12 months and then interim looks every half a year. For example, the anticipated start time for this study is December, 2012 and the expected end of subject enrollment is June, 2014. With 3 years follow-up time, the study is expected to be completed in June, 2017. Interim looks are planned for December 2013, June 2014, December 2014, June 2015, December 2015, June 2016, and December 2016, with a final look in June 2017. The stopping boundaries for effectiveness for these scheduled looks are displayed in the table below. At the time point of each interim analysis, the operating characteristics will be recalculated based upon the actual information fractions for the interim analyses already conducted and proportionally adjusted information fractions for all future interim analyses following methods described by Proschan, Lan and Wittes¹⁰. The software WinLD will be used. The approach implemented in the software WinLD takes into account calendar time as well as number of events. Calendar time scale will be used for the spending function. Number of events will be used to estimate covariance. At the time point of each interim analysis, boundaries will be re-estimated based on updated current calendar time estimate and actual number of events for all interim analyses up to the corresponding time point. The current calendar time estimate will be updated based on actual time point of current interim analysis, but using the maximum duration estimated at the time point of first interim analysis, thus previous estimates of calendar time will not change.

Operating Characteristics for Group Sequential Design

Look #	Intended Time after study start	Information Fraction	Number of Events	Stopping Bounds	Incremental Alpha	Cumulative Alpha
1	12 months	0.22	5	4.6374	0.00000	0.00000
2	18 months	0.33	9	3.7332	0.00009	0.00010
3	24 months	0.44	11	3.1913	0.00063	0.00073
4	30 months	0.56	15	2.8277	0.00192	0.00265
5	36 months	0.67	20	2.5881	0.00341	0.00606
6	42 months	0.78	22	2.3477	0.00499	0.01105
7	48 months	0.89	26	2.2183	0.00639	0.01744
8	54 months	1	28	2.0507	0.00756	0.02500

At any interim monitoring time t_j , we compute the Z statistic at information fraction t_j using the standardized logrank score statistic:

$$Z(t_j) = \frac{S(t_j)}{\sqrt{V(t_j)}}$$

where $S(t_j)$ is the observed logrank score statistic at time t_j , and $V(t_j)$ is the variance of $S(t_j)$. These statistics will be calculated using SAS PROC LIFETEST.

The Z test statistic will be compared with the stopping boundaries to determine whether this study will be stopped for effectiveness in each of the interim analyses. If the Z statistic crosses the stopping boundary, that is, Z is greater than the critical value at the interim look, then the study will be stopped for effectiveness. If the sample size exceeds the pre-planned sample size, then the CHW (Down-Weight) adaptive method will be used for statistical testing⁶ as detailed in section 6.

Conditional power will be calculated starting from first interim look to assist the determination of whether the study will be stopped for futility. SAS PROC SEQTEST will be used, with the expected effect size specified in section 6.

10.5 Sensitivity Analysis for the Primary Efficacy Variable

A sensitivity analysis will be performed using time to persistent AF (HRS 2017) as an alternative definition of the primary endpoint (see section 8.3). The analyses described in sections 10.1 to 10.3 will be repeated for this alternative definition. As this definition has not been investigated in any interim analysis, this sensitivity analysis will not need to be adjusted for interim looks. A one-sided alpha level of $\alpha=0.025$ will be used.

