2.2 Efficacy, Safety and Health Economic Endpoints

2.2.1 Efficacy Endpoints

The primary efficacy endpoint is the time to persistent AF/AT (excluding isthmus-dependent atrial flutter) at 3 years. According to the protocol, persistent AF/AT is defined as AF/AT lasting longer than 7 consecutive days or requiring termination by cardioversion after 48 hours.

Secondary efficacy endpoints are:

- Rate and time to persistent AF/AT at 1 year and 2 years, rate of persistent AF/AT by number of ablations at 3 years
- Number of repeat ablations and new anti-arrhythmic drugs (AAD) per subject throughout 3 years follow-up

- Rhythm (% subjects in sinus rhythm (SR), % subjects with recurrent AF/AT) throughout 3 years follow-up
- Factors associated with AF disease progression
 - Gender
 - Age
 - Left atrium (LA) size
 - HATCH score (score based on the five components: Hypertension, Age 75 years or older, Previous transient ischemic attack or stroke, Chronic obstructive pulmonary disease, and Heart failure)
 - Blood pressure
 - NYHA functional classification of heart disease
 - Presence of diabetes
 - Presence of hyperlipidemia or dyslipidemia
 - Presence of renal insufficiency
 - Presence of dementia

In addition, an alternative definition of the primary and the first secondary endpoint will be investigated based on the consensus statement of the HRS (Heart Rhythm Society, 2017). According to the HRS consensus statement 2017, persistent AF/AT is defined as continuous AF/AT that is sustained beyond 7 days.

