8.3 Derived Variables

Duration of AF [months]

Time between the recorded date of first AF and the date of randomization.

Time to persistent AF/AT

According to protocol, persistent AF/AT is defined as AF/AT lasting longer than 7 consecutive days or requiring termination by cardioversion after 48 hours. The primary endpoint is reached at the date of the first cardioversion after randomization (except cardioversion solely as part of a (re-)ablation procedure) or detection of persistent AF/AT by transtelephonic monitoring (TTM, performed between month 3 and month 36). The sponsor will review and adjudicate all events (progressions to persistent AF/AT), which were reported by the Investigator. Adjudication will already be performed for the interim analyses. All events where the sponsor confirmed in their final assessment that the primary endpoint was reached will be taken into account for analysis. The date at which the primary endpoint was reached will be taken as adjudicated by the sponsor or as reported by the Investigator (if no sponsor adjudicated date is available).

The protocol is not specific about the start date for time to event calculation. Originally according to SAP version 1.0 (which was applied for the interim analyses) time to event had been defined as the difference between randomization date and the date at which the endpoint was reached. However, after further discussion, it was decided to update the start date for time to event calculation for final analysis and to use date of procedure as start date for the test group, and date of randomization as start date for the control group.

This approach seems to be more appropriate and more conservative, as visit windows are calculated from date of procedure for test group. Otherwise, if time to event was calculated from date of randomization, test group would have longer follow-up period and longer time to each follow-up visit as control group.

If the primary endpoint is not observed during follow-up time, subjects will be regarded as censored at the completion visit/ last visit or at the last time TTM was recorded, whichever is later.

Time to persistent AF (HRS 2017)

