According to the HRS consensus statement 2017, persistent AF is defined as continuous AF that is sustained beyond 7 days. The sponsor will provide an additional adjudication using this alternative definition of time to persistent AF. Based on this additional adjudication, a sensitivity analysis for time to persistent AF based on HRS 2017 will be performed.

AFEQT

Several summary scores will be derived from the responses to questions 1 to 20 of section 2 of the AFEQT questionnaire, for each of which responses between 1 (most desirable outcome) and 7 (least desirable outcome) can be given.

Using the following statistics, the scores are defined below:

- $S(a,b)$ is the sum of responses for the range of questions between a and b (both a and b included)
- $N(a,b)$ is the number of responses given for the range of questions between a and b (both a and b included)
- AFEQT Overall Score = $100 - (((S(1,18) - N(1,18)) * 100) / (N(1,18) * 6))$
- AFEQT Symptoms Subscale Score = $100 - (((S(1,4) - N(1,4)) * 100) / (N(1,4) * 6))$
- AFEQT Daily Activities Subscale Score =
= $100 - (((S(5,12) - N(5,12)) * 100) / (N(5,12) * 6))$
- AFEQT Treatment Concern Subscale Score =
= $100 - (((S(13,18) - N(13,18)) * 100) / (N(13,18) * 6))$
- AFEQT Treatment Satisfaction Subscale Score =
= $100 - (((S(19,20) - N(19,20)) * 100) / (N(19,20) * 6))$

EQ-5D

The EQ-5D questionnaire collects the EQ-5D visual analogue scale (VAS) score on a scale between 0 and 100 and five single items (mobility, self-care, activity, pain, and anxiety) with three response levels each (no problems, some problems, extreme problems). A summary score (EQ-5D health index) based on these five items will not be calculated, as this would require rather complex modelling using country-specific weights.

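### SAP 10.5 gives a late-added HRS-2017 analysis its own ungated one-sided 0.025; the reason given for leaving it unadjusted does not support that

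*SAP*

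**What the plan says.** The primary event has two limbs (SAP 2.2.1 and 8.3): "persistent AF/AT is defined as AF/AT lasting longer than 7 consecutive days or requiring termination by cardioversion after 48 hours". The HRS-2017 event keeps only the first. SAP 8.3 words it as "persistent AF is defined as continuous AF that is sustained beyond 7 days" and SAP 2.2.1 as "According to the HRS consensus statement 2017, persistent AF/AT is defined as continuous AF/AT that is sustained beyond 7 days". HRS events come from an additional adjudication supplied by the sponsor (SAP 8.3), and the trial is open-label (SAP 3.4).

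SAP 10.5 repeats the analyses of 10.1 to 10.3, including the ITT log-rank test, under the HRS definition. Its last two sentences say that "As this definition has not been investigated in any interim analysis, this sensitivity analysis will not need to be adjusted for interim looks", and then set "A one-sided alpha level of" 0.025.

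For the primary endpoint, SAP 10.4 uses alpha spending so that "at the end of the study, the total Type I error does not exceed 0.025". SAP 5.1 allots the final primary test whatever alpha remains. It also says that the study ended early with neither the effectiveness nor the futility criterion met at the latest interim analysis. The HRS analysis is listed there among the changes for the final analysis and is called a sensitivity analysis. Neither document places it behind the primary test or says that it cannot support a claim.

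**The concern.** That a definition was not tabulated at interim does not make a test on it independent of the interim looks. Any episode that qualifies under HRS-2017 also qualifies under the primary definition. The two log-rank statistics therefore share events, and the primary statistic decided whether the trial continued.

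The practical stake is multiplicity. A purely descriptive analysis needs neither an alpha level nor an argument about interim adjustment, and 10.5 supplies both. If the primary test narrowly fails, a result under a definition chosen late, adjudicated separately and tested at a lower critical value could be reported as statistically significant. Nothing in the plan controls the error of the two tests together.

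**Working it through.** **Inputs from the SAP.** Example table in 10.4: events 5, 9, 11, 15, 20, 22, 26, 28; bounds 4.6374, 3.7332, 3.1913, 2.8277, 2.5881, 2.3477, 2.2183, 2.0507; total one-sided alpha 0.025. On timing, "Calendar time scale will be used for the spending function", with event counts used for the covariance. HRS test: Z > 1.96.

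**Assumption.** The share *f* of primary events that are also HRS events is not given. The main range is 0.5 to 0.9; 0.25 and 1 are shown as extremes.

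**Step 1: reproduce the plan's figure.** The O'Brien-Fleming-type spending function is 2[1 − Φ(z₀.₉₈₇₅/√t)], evaluated at calendar fractions 2/9, 3/9, …, 1, with correlations taken from the event counts. It gives cumulative alpha 0.01744 at look 7 (stated 0.01744), 0.0250 in total, and a final bound of 2.052 (stated 2.0507). Putting the stated bounds into a simulation returns 0.0250. The example design is reproduced.

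**Step 2: compare critical values.** One-sided p at 2.0507 is 0.0201; at 1.96 it is 0.0250. With fewer interims on the same calendar scale, the final primary bound comes out between 1.988 and 2.045 (p 0.0234 to 0.0204). The HRS test is the looser one in every case tried.

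**Step 3: simulate under the global null.** Write the primary score as S = S_H + S_C, where S_H (the >7-day limb) carries share *f* of the information and S_C (the cardioversion limb) carries 1 − *f*, independently. At any one look, corr(Z_primary, Z_HRS) = √f. A trial stops at the first primary crossing, and HRS is tested at 1.96 at that point or at the final look. Four million paths were run per value of *f*.

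| *f* | HRS own error, all paths | Primary fails, HRS significant | Either significant | Either, if HRS is held to 2.0507 without a gate |
|---|---|---|---|---|
| 1 | 0.029 | 0.004 | 0.029 | 0.025 |
| 0.9 | 0.029 | 0.008 | 0.033 | 0.030 |
| 0.75 | 0.028 | 0.012 | 0.037 | 0.034 |
| 0.5 | 0.027 | 0.017 | 0.042 | 0.038 |
| 0.25 | 0.026 | 0.021 | 0.046 | 0.041 |

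For example, at *f* = 0.5, 0.025 (primary) + 0.017 (HRS significant after the primary fails) = 0.042. If HRS is tested only after the primary succeeds, the middle term is zero and the total is 0.025.

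**Step 4: condition on no efficacy crossing.** This is closer to the course SAP 5.1 describes. Given no crossing at earlier looks, the error of the HRS test at 1.96, for *f* from 0.9 to 0.5, is:

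- at look 5: 0.023 to 0.024
- at look 7: 0.018 to 0.021
- at look 8: 0.014 to 0.019

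All are below 0.025, so the excess over 0.025 in the first error column of the table comes entirely from trials that cross an efficacy bound. At look 8 on this path, the primary test alone has a null chance of about 0.008 of being significant. With the ungated HRS test added, the chance of at least one significant result is about 0.016 (*f* = 0.9) to 0.025 (*f* = 0.5).

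**The case against.** The factual premise of 10.5, that this definition was not looked at during the trial, is contradicted nowhere. A reader might go further and infer that the interim looks inflated the HRS test's own error in this trial. The documents do not support that: SAP 5.1 reports no efficacy crossing, and Step 4 shows the error below 0.025 in that case. Tested once regardless of stopping, the HRS test has error 0.025, which is the sense in which the SAP's statement can be defended.

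A reader might also infer that the plan breaks a promise to hold 0.025 over both tests. It makes no such promise. SAP 10.4 gives 0.025 for the primary endpoint only, the HRS analysis is labelled a sensitivity analysis, and the SAP runs other ungated tests (the per-protocol analysis in 10.2, and log-rank tests at 1 and 2 years in 10.6.1). Nor does the SAP say that the HRS result would be promoted to a claim.

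Finally, nesting holds for qualifying conditions, not necessarily for event dates. A subject cardioverted after 48 hours has the primary event on that date. Any AF beyond 7 days would come later, and might go unseen because the protocol stops transtelephonic monitoring once the primary endpoint is reached (Protocol 11.2.1). The √f model is therefore an approximation.

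These points limit the finding to multiplicity and late addition. They do not rescue the inference in 10.5, and the sensitivity label sits poorly with an explicit alpha level and no gate.

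**Conclusion.** The point holds as a multiplicity and late-addition problem. The reasoning in 10.5 is unsound as a general rule, because the HRS condition is part of an endpoint that was monitored and governed stopping for effectiveness. As written, a late-added test receives a full, ungated 0.025 at a lower critical value than the primary. In the example design under the global null, the chance that at least one of the two is significant is about 0.042 to 0.033 for HRS shares of 50% to 90%, against 0.025 for the primary alone. The HRS test's own error averages about 0.027 to 0.029 over all paths, but about 0.014 to 0.024 at looks 5, 7 and 8 given no crossing.

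The figures rest on the assumed share, nested event timing and the example look schedule. The actual looks and the remaining alpha are not in the documents, and an early termination that depended on the data was not modelled. The primary test itself is unaffected. The change should be made, but the primary conclusion does not depend on it.

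**What to change.** Delete the last two sentences of SAP 10.5. Replace them with one of two statements:

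- the HRS-2017 result is supportive only, reported as a hazard ratio with confidence interval and no significance claim; or
- the HRS-2017 test is carried out only if the primary test succeeds (fixed sequence).

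Apply the same wording to the HRS repeats of the secondary analyses in SAP 10.6.1. Giving HRS the primary's critical value without the gate is not enough: the chance of at least one significant result stays at about 0.030 to 0.038 for shares of 90% to 50%.

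The cost is two sentences in 10.5, matching wording in 10.6.1, and the loss of a stand-alone HRS significance claim. No data collection or adjudication changes.
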